### 8.3. Biomarkers

#### 8.3.1. Primary Analysis of Exploratory Biomarkers

Biomarker endpoints include the following:

- Change from baseline in hemoglobin (Hb) at Weeks 4, 8 and 12
- Proportion of patients with change from baseline in Hb  $>1$  g/dL at end of treatment
- Change from baseline in fetal hemoglobin (HbF) at Weeks 4, 8 and 12

Blood and urine samples for assessments of PD effects will be collected according to the applicable event schedule in Table 5a and 5b.

For each available biomarker, the observed value and the change from baseline (if applicable) will be summarized using descriptive statistics by treatment group and applicable time point.

The biomarkers of interest include LDH, reticulocyte count, bilirubin, Hb, HbF, haptoglobin, cystatin-C, urinary albumin and creatinine ratio (UACR), soluble E-selectin, soluble P-selectin, L-selectin, platelet monocyte aggregation, VCAM and ICAM.

Specifically, the following key biomarker responders for Hb and HbF will be summarized for each available visit and EOT.

1. Proportion of participants with increase from baseline in Hb  $>1$  g/dL
2. Proportion of participants with change from baseline in HbF  $>3\%$  points
3. Proportion of participants with increased change from baseline in HbF and HbF  $>8\%$

For each of the key biomarkers (Hb and HbF), the observed value and the changes from baseline will be summarized by treatment group and available visit. In addition, ANCOVA model mentioned in [Section 8.1](#) will be fitted to estimate the difference in change from baseline between each olinciguat group and the placebo group, for each available visit.

The proportion of biomarker responders specified above will be summarized by treatment group. In addition, a Cochran-Mantel-Haenszel (CMH) test (mentioned in [Section 8.2](#)) will be used to estimate the difference in the proportions for each olinciguat treatment group and the corresponding placebo group.

#### 8.3.2. Sensitivity Analysis of Key Biomarkers

In addition, the following sensitivity analyses will be conducted for changes from baseline of Hb and HbF and proportions of biomarker responders specified above, using the Safety Population.

- Summary using descriptive statistics for participants enrolled under Protocol Amendment 4 or later, with PBO2, and 18 mg olinciguat (split into 6 mg, 12 mg, 18 mg groups based on the last uptitration).
- Mixed-effect model for repeated measures (MMRM) will be fitted with change from baseline as dependent variable, treatment group, visit, the interaction between treatment and visit and

This document is confidential.

stratification factor (HU use) as categorical variables, and corresponding baseline value as covariate. For each available visit, LSMs for each treatment group, LSM differences between each olinciguat group and the placebo group, their corresponding 2-sided 95% CIs, and p-values will be presented. An unstructured covariance matrix will be used to model the correlation among repeated measurements. MMRM models will use data available from the Weeks 1, 4, 8 and 12 visits.

## 8.4. Patient-reported Outcomes

### 8.4.1. Sickle Cell Disease – Symptom Assessment Form (SCD-SAF)

#### 8.4.1.1. Primary Analysis of SCD-SAF

The SCD-SAF endpoints are listed here:

- Changes from baseline in SCD-SAF total score at Weeks 4, 8, 12, and EOT
- Pain as measured on the 11-point numerical rating scale (NRS) by week and for the overall Treatment Period
- Percent change from baseline in pain as measured on the 11-point NRS by week and for the overall Treatment Period
- Change from baseline in pain as measured on the 11-point NRS by week and for the overall Treatment Period
- Change from baseline in fatigue as measured on the 11-point NRS by week and for the overall Treatment Period

The SCD-SAF will assess sickle cell-related symptoms, including an assessment of pain on an 11-point numerical rating scale (NRS) (0 [no symptom] to 10 [worst possible symptom]), using a daily eDiary by participants. Depending on the version of SCD-SAF used by the participant, 7 questions (Version 1) or 8 questions (Version 2) about the symptoms over the past 24 hours are asked, including the worst pain, the worst fatigue, the worst swelling, the worst numbness, the worst tingling (Version 2 only), the worst stiffness, shortness of breath, and difficulty concentrating. If 8-question SCD-SAF (Version 2) is used, SCD-SAF total score is the sum of the 8 sub-scores. If the 7-question SCD-SAF (Version 1) is used, SCD-SAF total score is the sum of the 7 sub-scores multiplied by (8/7). If any individual score is missing, the total score is set as missing. Individual scores include pain sub-score, fatigue sub-score, swelling sub-score, numbness sub-score, tingling sub-score, stiffness sub-score, shortness of breath sub-score, difficulty concentrating sub-score.

The baseline NRS will be determined based on the average of available daily NRS data during the 7 days prior to randomization. The weekly NRS scores are calculated as the average of available daily NRS scores for each week postdose (Week 1 = Day 1 to 7, Week 2 = Day 8 to 14...). The EOT NRS score is the last weekly NRS score collected after the first dosing date and through the last dosing date plus 4 days.

For each mean daily NRS score (total score, each individual score, subtotal score of pain + stiffness + fatigue), the observed value, the changes from baseline, and the percentage change from baseline will be summarized by treatment group and visit. In addition, ANCOVA model mentioned in [Section 8.1](#) will be

This document is confidential.

fitted to estimate the difference in change from baseline/percent change from baseline of total score/sub-score between each olinciguat group and the placebo group, at each visit.

For the proportion of participants with daily pain response (defined as achieving at least a 30% reduction in average daily pain from baseline) at Week 12, the number and percentage of participants will be summarized by treatment group. Besides, a Cochran-Mantel-Haenszel (CMH) test (mentioned in [Section 8.2](#)) will be used to estimate the difference in the proportions for each olinciguat treatment group and the corresponding placebo group.

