## 8. Pharmacodynamic (PD) Analyses

All PD analyses except the PRO analyses will be based on the Safety and Evaluable Populations. PRO analyses will be based on the ITT and Evaluable Populations. Listings will be provided for all PD-related data.

For the treatment comparisons by statistical modeling:

- comparisons between 18 mg olinciguat group vs. the matched placebo group (PBO2) enrolled under Protocol Amendments 4 and later
- comparisons between each olinciguat group (2 mg, 4 mg, 6 mg, and 18 mg) vs. the overall placebo group combined from all protocols

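### The SCD-SAF total is an 8-item sum for some participants and a rescaled 7-item sum for others, with no version term in the models, so any contrast with unbalanced versions carries an instrument effect

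*SAP*

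**What the plan says.** **Forms and scoring (SAP 8.4.1.1).** Version belongs to the participant: "Depending on the version of SCD-SAF used by the participant, 7 questions (Version 1) or 8 questions (Version 2". Items run from 0 to 10 ("0 [no symptom] to 10 [worst possible symptom"). The one item that differs is "the worst tingling (Version 2 only". For the longer form, "If 8-question SCD-SAF (Version 2) is used, SCD-SAF total score is the sum of the 8 sub-scores". For the shorter form, "If the 7-question SCD-SAF (Version 1) is used, SCD-SAF total score is the sum of the 7 sub-scores multiplied by (8/7". For a blank item, "If any individual score is missing, the total score is set as missing".

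**Endpoint.** "Changes from baseline in SCD-SAF total score at Weeks 4, 8, 12, and EOT" is the first SCD-SAF endpoint in SAP 8.4.1.1 and heads the exploratory patient-reported outcomes in Table 1 of SAP 3.1.

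**Models.** The total is analysed with the ANCOVA of SAP 8.1 (treatment, hydroxyurea stratum, baseline) and, in SAP 8.4.1.2, with the MMRM of SAP 8.3.2, which adds visit and treatment-by-visit. Neither model has a term for version or amendment, and no analysis of the total is restricted by version.

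**Contrasts (SAP section 8).** One compares 18 mg with PBO2, the placebo group from Amendment 4 onward. The others are "comparisons between each olinciguat group (2 mg, 4 mg, 6 mg, and 18 mg) vs. the overall placebo group combined from all protocols".

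**What is not stated.** Neither document says which version was used under which amendment, or whether a participant could switch. Protocol 3.8.9.1.1 describes a single instrument, and Protocol 5.10.2.1 leaves the data handling to the SAP. SAP section 11 does not mention the rescaling.

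**The concern.** One endpoint name covers two constructions. Multiplying a 7-item sum by 8/7 amounts to filling in the tingling score with the mean of the other seven items, at baseline and at every later week. The SAP gives no reason to expect tingling to track that mean.

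This does no harm when both arms of a contrast have the same mix of versions and tingling moves alike in each, because a common discrepancy then cancels. When the mix differs, part of the estimated treatment difference reflects which form was used. Randomisation is stratified by hydroxyurea use only (SAP 3.5), so balance on version is not designed in, and combining placebo over all protocols is where an imbalance could enter.

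If version changed with the amendment, 2, 4 and 6 mg would have no like-for-like modelled comparison, because SAP section 8 plans no model contrast of those doses with the earlier placebo group (PBO1) alone.

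**Working it through.** **Inputs.** Item range 0–10 and the two scoring rules (SAP 8.4.1.1). Planned numbers of about 40 and 48 (SAP 3.4). Allocation 1:1:1:1 up to Amendment 3 and 3:1 from Amendment 4 (SAP 3.2). The documents give no item means, SDs or effect sizes, so the values of d and the item scores below are assumptions.

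**1. The plan's factor.** Version 1 maximum: 7 × 10 × 8/7 = 80. Version 2 maximum: 8 × 10 = 80. The factor does equalise the range.

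**2. Content.** Let M be the mean of the seven common items and T the tingling score.
- Version 1 total = 8M; Version 2 total = 7M + T.
- Difference = M − T.
- Extreme days: with the seven items at 10 and T = 0, the totals are 80 and 70. With the seven at 0 and T = 10, they are 0 and 10.

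**3. Change from baseline.** Define d = (change in T) − (change in M). Then Version 1 change = Version 2 change − d. Example with the seven items each falling from 4 to 3:

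| Tingling | Version 1 change | Version 2 change |
|---|---|---|
| 0 to 0 | −8.0 | −7.0 |
| 4 to 4 | −8.0 | −7.0 |
| 4 to 3 | −8.0 | −8.0 |
| 6 to 4.5 | −8.0 | −8.5 |

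**4. Effect on a contrast.** Take d as equal in all arms, and let f be the share of an arm on Version 1. The artefact in active minus placebo, on unadjusted change, is (−d × f_active) − (−d × f_placebo) = d × (f_placebo − f_active). Equal shares give zero.

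**5. One assumed mapping: Version 1 up to Amendment 3, Version 2 from Amendment 4.** Planned placebo: 40/4 = 10 and 48/4 = 12, so 22 pooled. Planned 18 mg: 48 × 3/4 = 36. Check: 4 × 10 + 12 + 36 = 88, as planned.
- 18 mg vs PBO2: d × (0 − 0) = 0.
- 18 mg vs pooled placebo: d × (10/22 − 0) = +0.45d.
- 2, 4 or 6 mg vs pooled placebo: d × (10/22 − 1) = −0.55d.
- For d from −2 to +2: −0.91 to +0.91 for 18 mg, and +1.09 to −1.09 for the lower doses, on the 80-point scale.

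A positive value counts against olinciguat, since a fall is improvement.

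**6. Baseline adjustment.** Suppose every item falls 30% from a common-item mean of 3.
- Version 1: 24, change −7.2.
- Version 2 with tingling 0.5: 21.5, change −6.45. With tingling 2: 23, change −6.9.
- Unadjusted artefact for 18 mg: 10/22 × 0.75 = 0.34 and 10/22 × 0.30 = 0.14.
- Each change is exactly −0.3 times its own baseline, so percent change is −30% in both versions and a noiseless ANCOVA absorbs the artefact completely.
- Simulating this case (tingling 0 to 2, between-patient SD 1.2 and noise SD 0.5 to 1.0 on the seven-item mean, all assumed) gives an adjusted shift of about −0.03 to −0.43. The sign is opposite to the unadjusted one, and the SD of the estimate is 1.2 to 2.3.
- Adjustment does not always help. In the row of step 3 where tingling stays at 4, both versions start at 32 but change by −8 and −7. Baseline cannot separate them, and about 0.45 × 1 = 0.45 remains.

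**The case against.** Several points on the other side stand.

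- The pooling in SAP section 8 is over protocols. A reader might infer that it is therefore known to be over versions. The documents do not show that, because version is never tied to amendment or arm.
- If version does follow amendment, the first contrast listed, 18 mg vs PBO2, is like-for-like.
- A reader might take the unadjusted 0.1 to 0.4 points of the proportional-fall example as a bias against 18 mg. The planned baseline-adjusted model does not support that: the shift is zero without noise and small, with the other sign, once noise is added.
- A reader might also see a contradiction between discarding a Version 2 day with tingling blank and accepting every Version 1 day without it. That does not follow. An item that is not on the form is different from one that was asked and left blank, and the missing-item rule treats the items each form asks alike. Weekly scores average the available days, so one lost day does not lose the week.
- Pain, fatigue, stiffness and their subtotal contain no tingling and are analysed in their own right. SAP 8.4.1.2 also has a descriptive summary of the total limited to Amendment 4 or later.
- The proration is prespecified and transparent, safety is the primary objective, and the total is exploratory.

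These points limit the size and reach of the problem. They do not make the two totals the same quantity, and no planned analysis of the total checks whether version matters.

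**Conclusion.** The point holds in conditional form. That the two totals differ in content is certain from the scoring rules. That a particular contrast mixes them is not, because the version-to-arm mapping is missing. Any contrast with unequal version shares includes an instrument effect unless tingling changes as the other items do on average.

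Under the assumed mapping by amendment, and with d the same in every arm, the effect on unadjusted change is zero for 18 mg vs PBO2, about +0.45d for 18 mg vs pooled placebo, and about −0.55d for each lower dose. That is about 1 point or less of 80 for |d| up to 2. Under the planned ANCOVA the sign and size are uncertain and can be near zero. The documents do not support a claim of known bias for or against any dose, nor a need to abandon the 8-item total. This is a worthwhile, low-cost improvement to an exploratory endpoint.

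**What to change.** In SAP 8.4.1.1 and 8.4.1.2:

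- Add an analysis of the total scored on the seven items common to both versions, for all participants (range 0–70), with the missing-item rule applied to those seven and the same ANCOVA and MMRM. Rely on it for any contrast that mixes versions. Its version difference is zero by construction, whatever the mapping.
- Keep the 8-item total and the tingling sub-score for contrasts within Version 2 users.
- Tabulate SCD-SAF version by amendment and arm, so that the reader can see which contrasts are mixed.

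The cost is one more derivation and set of tables, and tingling does not contribute to the mixed-version contrasts.

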9. Female patient must be postmenopausal (no menses for ≥ 12 consecutive months) or surgically sterile (ie, bilateral oophorectomy, hysterectomy, or tubal sterilization [tie, clip, band, or burn]); must agree to completely abstain from heterosexual intercourse; or, if heterosexually active, must agree to use 1 of the following methods of birth control from the date she signs the informed consent form (ICF) until 90 days after the final dose of study drug:

- Progesterone implant and/or an intrauterine device (IUD)
- Combination of 2 highly effective birth control methods (eg, diaphragm with spermicide plus a condom, condom with spermicide plus a diaphragm or cervical cap, hormonal contraceptive [eg, oral and transdermal patch] plus a barrier method, or partner with vasectomy [conducted ≥ 60 days before the Screening Visit or confirmed via sperm analysis] plus a hormone or barrier method).

10. Male patient must be surgically sterile by vasectomy (conducted ≥ 60 days before the Screening Visit or confirmed via sperm analysis), must agree to completely abstain from heterosexual intercourse, or, if heterosexually active, must agree to use a combination of 2 highly effective birth control methods (eg, partner use of progesterone implant and/or IUD, condom with spermicide plus a partner diaphragm or cervical cap, partner hormonal contraceptive [including progesterone implant] plus a barrier method, or postmenopausal partner [for ≥ 1 year] plus barrier method) from the Screening Visit through 90 days after the final dose of study drug.

11. Patient is fluent in the language of the local ICF (eg, English, Spanish, Arabic, French).

12. Patient completes daily eDiary entries for at least 10 days during the last 14 days of the Run-in Period as assessed at the Randomization Visit. (Note: To enter the Run-in Period, patient must meet all eligibility criteria applicable to the Screening Visit.)

EXCLUSION CRITERIA

Patients who meet any of the following criteria will not be eligible to participate in the study:

1. Patient requires a program of prescheduled, regularly administered chronic blood transfusion therapy, has received a transfusion in the 8 weeks before the Randomization Visit, and/or is scheduled to receive a transfusion during the study.
2. Patient has been hospitalized for an SCD-related complication in the 4 weeks before the Randomization Visit.

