- Run-in Period:** The single-blind Run-in will begin at least 3 days after the Screening Visit and is defined as the 14 to 17 days before the first dose of double-blind study drug on Day 1. At the Run-in Visit, eligible patients will take their first single-blind (placebo) dose in the clinic, will undergo safety and pharmacodynamic (PD) assessments, and will complete patient-reported outcome (PRO) questionnaires in an eDiary (a handheld personal electronic device) that will be issued for their use. They will continue to take once-daily single-blind placebo at home and will record daily and weekly assessments in their eDiary throughout this period. Patients will be required to complete at least 10 days of daily assessments during the final 14 days of the Run-in Period to remain eligible for randomization into the Treatment Period.

Treatment Period: The double-blind Treatment Period will begin on Day 1 at Randomization (there is no Day 0) and will end after the End-of-Treatment (EOT) Visit on Day 85 (-7/+4).

Eligible patients will take their first dose of double-blind study drug in the clinic on Day 1 and will undergo safety, PRO, PK, and PD assessments at prespecified times according to the [Schedule of Events](#). Patients must remain in the clinic at least 6 hours postdose and thereafter will be allowed to leave at the Investigator's discretion. Starting on Day 2, patients will take their daily double-blind study drug dose at home, per Section [3.5.4.1](#). Also on Day 2, preferably in the afternoon, patients will receive a phone call for adverse event (AE) and concomitant medication and procedure(s) assessment. Throughout the Treatment Period, patients will continue to record daily assessments in their eDiary.

At their Week 1 (Day 8 [± 1]) and Week 4 (Day 29 [± 3]) visits, respectively, patients who meet the uptitration criteria (see Section [3.5.4.2](#)) will begin taking the applicable higher dose. At these visits, patients must again stay in the clinic at least 6 hours postdose to undergo safety, PRO, PK, and PD assessments at prespecified times according to the [Schedule of Events](#) and thereafter will be allowed to leave at the Investigator's discretion. On the day after these 3 visits, preferably in the afternoon, patients will receive a phone call for assessment of AEs and concomitant medication(s) and procedure(s).

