3.2 DISCUSSION OF STUDY DESIGN

A double-blind, placebo-controlled, randomized study design was chosen to provide comparable treatment groups and to minimize chance of selection or Investigator bias in accordance with the concepts in ICH E10, Choice of Control Groups and Related Issues in Clinical Trials (International Conference on Harmonisation of Technical Requirements for Registration of Pharmaceuticals for Human Use, 2001). Placebo was chosen as the control so that the rate of spontaneously occurring AEs can be determined and to reduce the potential for bias in the reporting of AEs.

The 2-week Run-in portion of the Screening Period will establish baseline values for daily and weekly patient-reported assessments. Treatment with single-blind placebo during this period will provide data on potential placebo response, and, in addition, will identify patients with low study drug/eDiary adherence who may benefit from retraining efforts.

The 12-week Treatment Period will compare the effects of IW-1701 with those of the placebo control. This length is sufficient to assess safety and tolerability, changes in patient-reported sickle cell-related symptoms, and changes in levels of biomarkers related to the NO-sGC-cGMP pathway.

Patients will be stratified by HU use (yes or no) to ensure equal allocation across treatment arms within stratum, which serves to control any potentially confounding influence (eg, difference in treatment response in patients taking HU).

Data Monitoring Committee (DMC) safety reviews (Section 3.7) will ensure that dosing will stop should a safety signal be detected. Patients will have a Follow-up Visit 28 (-3/+7) days after the final dose of study drug to determine if any AEs have developed and if AEs that were ongoing at the EOT Visit have resolved.

At each scheduled study visit, including the final Follow-up, women of reproductive potential will have a pregnancy test; results will be reviewed and documented prior to each in-clinic study drug administration, as applicable. Patients of both sexes will be instructed to follow the contraception requirements listed in Section 3.6.4.

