#### 8.4.4. Analgesic Use

The analgesic use endpoint is the number and percentage of days with analgesic use at Week 4, 8, and 12.

Participant will be asked to record use of pain medication (names of medications) using a daily eDiary by participants.

The baseline number (percentage) of days with analgesic use will be determined based on records during the 7 days prior to randomization. The weekly number (percentage) of days with analgesic use are calculated based on the records during each week postdose (Week 1 = Day 1 to 7, Week 2 = Day 8 to 14...). If the number of days with non-missing data per period is not 7, the weekly percentage of days with analgesic use will be derived based on the records with non-missing data; the weekly number of days with analgesic use will be normalized to a 7-day period (ie,  $7 * \text{weekly percentage of days with analgesic use}$ ).

For the number (percentage) of days with analgesic use, the observed value and the changes from baseline will be summarized using descriptive statistics by treatment group and visit. In addition, the proportion of participants with any analgesic use during the week will be summarized as a responder endpoint.

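### The SCD-SAF baseline averages whatever diary entries fall in the last 7 run-in days, with no minimum or fallback, so an eligible patient's baseline can rest on as few as 3 entries

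*SAP*

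**What the plan says.** SAP 8.4.1.1 defines the diary baseline as follows: "The baseline NRS will be determined based on the average of available daily NRS data during the 7 days prior to randomization". Post-baseline scores use the same approach: "The weekly NRS scores are calculated as the average of available daily NRS scores for each week postdose". Neither sentence gives a minimum number of days or says what to do when the window is sparse. The same section sets a day's total score to missing if any item is missing.

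The protocol's entry rule uses a longer window. Inclusion 12 reads "Patient completes daily eDiary entries for at least 10 days during the last 14 days of the Run-in Period as assessed at the Randomization Visit", and Section 3.1 repeats it without any condition on where the days fall. Section 3.1 places the Run-in: it "is defined as the 14 to 17 days before the first dose of double-blind study drug on Day 1". Section 3.2 gives one of its purposes: "The 2-week Run-in portion of the Screening Period will establish baseline values for daily and weekly patient-reported assessments". SAP 6.6 also treats the single-blind run-in as the baseline period when it summarizes diary compliance.

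This baseline is the covariate in the ANCOVA (SAP 8.4.1.1) and in the MMRM sensitivity analysis (SAP 8.4.1.2). It is also the reference for change, percent change and the 30% pain response at Week 12.

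**The concern.** The entry rule and the baseline derivation use different windows, and nothing links them. A patient can satisfy Inclusion 12 mainly through the first of the two weeks and then contribute a baseline built on a few days of the second. The plan already holds usable entries for that patient, recorded on placebo before randomization, but the derivation ignores them.

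Precision is what is at stake. A mean of few days is a noisier covariate, so ANCOVA and MMRM remove less variance. Percent change and the 30% response divide by this baseline, so noise in it also moves individual patients across the response threshold. The planned arms are small: about 10 per arm under Amendment 3 (40 patients, 1:1:1:1), then about 36 and 12 (48 patients, 3:1).

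**Working it through.** The documents give no precision figure for the diary baseline, so there is none to reproduce. The check is a count followed by illustrations.

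**1. Smallest possible baseline.** The inputs are at least 10 entries in 14 days (Inclusion 12) and a baseline window of the last 7 days (SAP 8.4.1.1). The first 7 days can hold at most 7 entries, so the last 7 hold at least 10 − 7 = 3. In that case 7 run-in entries are unused. With 11, 12, 13 or 14 completed days the minimum is 4, 5, 6 or 7.

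**2. How often, at exactly 10 of 14.** Assume the completed days fall at random. Then P(k in last 7) = C(7,k) × C(7,10−k) / C(14,10), with C(14,10) = 1001.

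| Entries in last 7 days | Patterns | Share |
|---|---|---|
| 3 | 35 | 3.5% |
| 4 | 245 | 24.5% |
| 5 | 441 | 44.1% |
| 6 | 245 | 24.5% |
| 7 | 35 | 3.5% |

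Three or four entries: 280/1001 = 28%.

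**3. How often, among all eligible patients.** Assume each day is completed independently with probability p, and condition on at least 10 of 14.

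| p | 3 entries | 3 or 4 entries |
|---|---|---|
| 0.80 | 0.7% | 8.3% |
| 0.85 | 0.4% | 5.0% |
| 0.90 | 0.1% | 2.1% |
| 0.95 | 0.01% | 0.4% |

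The documents give no completion rate. Missed days that cluster before randomization would raise these shares.

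**4. Precision of one patient's baseline.** With independent days, SE = (within-patient daily SD)/√m. This is 0.58 SD for m = 3 and 0.38 SD for m = 7, a ratio of √(7/3) = 1.53. With day-to-day AR(1) correlation of 0.5 (assumed), SE² = (1/m²) ΣΣ 0.5^|i−j| in SD² units. Three evenly spread days in the week give √[(3 + 4×0.125 + 2×0.0156)/9] = 0.63, three consecutive days 0.78, and a full 7-day week 0.59. With correlated days, the loss depends mainly on whether the few entries are bunched.

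**5. Effect on ANCOVA.** Take reliability R(m) = mρ/(1 + (m−1)ρ), where ρ is the correlation between days. The residual SD is then proportional to √(1 − r²R(m)R(7)), where r is the true correlation between baseline and outcome. Assume ρ = 0.3 to 0.7 and r = 0.6 to 0.9.

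- Example at ρ = 0.5, r = 0.9: R(3) = 0.75, R(5) = 0.833 and R(7) = 0.875. The residual terms are 0.684, 0.640 and 0.616 for m = 3, 5 and 7.
- At the eligibility minimum the mean count in the last week is 10 × 7/14 = 5. If every patient had 5 entries rather than 7, the residual SD would be about 0.5% to 4% larger.
- If every patient had only 3, it would be about 2% to 11% larger.

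**6. Effect on the 30% response.** Assume a normal approximation, independent days, no true change, and 7 entries at Week 12. The chance of a false response is Φ[−0.3μ / (σ√(1/7 + 0.49/m))]. For assumed true pain μ = 4 to 5 and daily SD σ = 1.5 to 2, this is 3.5% to 14% with m = 3 and 1.5% to 10% with m = 7.

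**The case against.** The strongest defence is that the 7-day window is coherent. Post-baseline scores are 7-day means of available entries, also with no minimum, so baseline and outcome are built alike. That stands: the window length is not the fault, and a 14-day mean would be a trade-off rather than a correction. What it does not answer is the missing minimum or fallback when usable entries lie just outside the window.

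It also stands that sparse baselines should be uncommon, that the endpoints are exploratory, and that the loss is small on average.

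A reader might infer four stronger points, which the documents do not support.

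- *That the SAP shortened an agreed 14-day baseline without declaring it.* The protocol never specifies a 14-day mean. Section 3.2 says only that the run-in establishes baseline, the last 7 days lie within it, and protocol Sections 5.1 and 5.10.2.1 leave data handling to the SAP.
- *That Inclusion 12 exists to secure the baseline.* No rationale is given for it. Section 3.2 also names placebo response and finding patients with low diary adherence as purposes of the run-in, and a 10-of-14 rule fits an adherence screen.
- *That the treatment comparison is biased.* The baseline precedes randomization, so its error has the same distribution in every arm randomized together. Precision falls, and responder misclassification blurs a difference rather than creating one.
- *That the analgesic-use baseline needs the same change.* In SAP 8.4.4 it "will be determined based on records during the 7 days prior to randomization", but that analysis is descriptive and already normalizes incomplete weeks to 7 days. A longer window would also make any analgesic use mechanically more likely at baseline than in a post-baseline week.

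Finally, the 10-of-14 rule is visible only in Amendment 5. The diary rule for the roughly 40 of 88 patients randomized under Amendment 3 or earlier is not shown, so the guaranteed minimum of 3 cannot be claimed for them.

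**Conclusion.** The point holds as a cheap improvement to an exploratory analysis. SAP 8.4.1.1 allows a baseline from as few as 3 entries in a patient who meets the Amendment 5 diary rule, while up to 7 placebo run-in entries are unused. The count is exact. The 28% figure applies only to patients at exactly 10 of 14 with days completed at random; across all eligible patients, assumed completion of 80% to 95% gives about 8% down to 0.4% with 3 or 4 entries. The precision figures rest on assumed day-to-day SDs and correlations, since the documents give none.

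For the total score the usable count could fall below 3 if a diary day with a missing item counts toward eligibility; the documents do not settle this. The primary safety endpoint is unaffected.

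**What to change.** In SAP 8.4.1.1, replace the baseline sentence with a rule of this kind: *for each SCD-SAF score, baseline is the mean of the last 7 completed daily entries within the final 14 days of Run-in; if fewer than 7 are available in that window, all available entries are used.* For the total score, count an entry as completed only if every item needed for that day's total is present.

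This keeps a 7-entry basis to match the weekly scores and leaves patients with a complete last week unchanged. Every patient with 10 complete entries in the last 14 days gets a full 7. The fallback covers patients under earlier amendments, whose diary rule is not shown.

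The cost is one SAP sentence and one derivation change before unblinding, with no new data. The downside is that some baseline entries will be up to a week older, though still on placebo run-in. Leave SAP 8.4.4 as it is. An entry in SAP Section 11 is optional, because the protocol states no explicit averaging window.
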